7.2.4 Previous and Concomitant Medications

Medications will be coded with World Health Organization Drug Dictionary (WHO-DD)

(September 2016, HD Format B2).

Previous medication is defined as medication with at least one dose taken before initial study treatment. Number and percentage of subjects taking the previous medication by treatment arm for the ITT/SAF population.

Concomitant medication for 1st line is defined as medication with at least one dose taken between the date of first dose (inclusive) and the date of last dose of study drug for 1st line AAT and the date of first dose (not inclusive) of study drug for 2nd line AAT. Concomitant medication for 2nd line is defined as medication with at least one dose taken between the date of first dose (inclusive) and the date of last dose of study drug for 2nd line AAT and the date of safety visit (inclusive). As with previous medications, number and percentage of subjects taking the concomitant medication by treatment arm for the ITT/SAF population.

Number of subjects with at least one previous and concomitant medications will be summarized

Data listings will be presented for previous and concomitant medications and therapies.

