Treatment duration of bicalutamide (Months)=(End date of bicalutamide - Start date of bicalutamide + 1) / 30.4375

Previous and concomitant medication

Previous medication is defined as medication with at least one dose taken 4 weeks (28 days) before Day 1 to the day before initial study treatment.

Sponsor: Astellas Pharma Inc. SAP Version 1.00

ISN/Protocol 9785-MA-3051

Concomitant medication for 1st line is defined as medication with at least one dose taken between the date of first dose (inclusive) of study drug for 1st line AAT and the date of first dose (not inclusive) of study drug for 2st line AAT.

Concomitant medication for 2nd line is defined as medication with at least one dose taken between the date of first dose (inclusive) of study drug for 2nd line AAT and the date of safety visit (inclusive).

Concomitant medication through study medication is defined as medication with at least one dose taken between of first dose (inclusive) and the date of safety visit (inclusive).

PSA doubling time (PSADT)

PSA doubling time is defined from two consecutive PSA measurements (PSA_1, PSA_2) and measured dates (Day_1, Day_2) before study Day 1 as follow;

PSA doubling time (month) =
$$\frac{\ln(2) * 12}{365.25 * \frac{\ln(PSA_2) - \ln(PSA_1)}{Day_2 - Day_1}}$$

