The treatment-emergent period will be defined as the period of time from the date of the first dose of study drug to 28 days after the date of the last dose of study drug, or 1 day prior to the date of initiation of cytotoxic chemotherapy for prostate cancer or an investigational agent treating prostate cancer, whichever occurs first. And 1st line treatment-emergent period is defined as the period of time from the date of the first dose of study drug in 1st line to 28 days after the date of the last dose of study drug in 1st line, or 1 day prior to the date of initiation of cytotoxic chemotherapy for prostate cancer or an investigational agent treating prostate cancer, whichever occurs first. Regarding 2nd line treatment-emergent period is applied same rule for 2nd line date.

• Baseline Value and Post-Baseline Value

Unless otherwise specified, the baseline value is defined as the last non-missing measurement prior to the randomization of study drug. When analysis be provided separately by treatment lines, baseline value for 2nd line AAT is defined as the last non-missing value measurement prior to the enrollment for 2nd line AAT of study drug.

Post-baseline value is defined as a measurement taken after the randomization of study drug. For Post-baseline value for 2nd line is defined as a measurement taken after enrollment during of study for 2nd line AAT.

Baseline value is defined as the last non-missing measurement prior to randomization (or register of 2nd line AAT) and post-baseline value is defined as a measurement taken after randomization for subjects who did not receive study drug. Change from baseline is defined as (post-baseline value - baseline value). Both date and time of drug administration and measurement should be considered when calculating baseline value. If time is not available, then date only should be used.

Treatment Group

Treatment group is defined as planned randomized treatment sequence which divide to initial enzalutamide 160 mg/day group or the initial flutamide 125 mg × 3 times daily (375 mg/day) group.

• Treatment Arm

Treatment arm is defined as administration drug group regardless 1st line or 2nd line treatment. That is enzalutamide plus ADT arm include subject who receive enzalutamide plus ADT at 1st line and 2nd line. Flutamide plus ADT include who receive flutamide plus ADT at 1st line and 2nd line.

• Treatment Line

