7.2.5 Previous Therapies for Prostate Cancer

Previous therapies for prostate cancer will be summarized by treatment group as randomized for the ITT population and SAF population as follows:

- Summary statistics for treatment duration of bicalutamide
- Number of subjects with gonadotropin releasing hormone (GnRH) agonist / antagonist and each drug
- Number of subjects with other drug therapies
- Number of subjects with radiation therapy

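### SAP 7.2.4 tabulates previous medications by drug received in either line, so subjects who switch count in both columns and the table does not compare the randomized groups.

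*SAP*

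**What the plan says.** SAP 7.2.4 gives the table for previous medications as "Number and percentage of subjects taking the previous medication by treatment arm for the ITT/SAF population".

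SAP 7.1.2 defines two terms that sound alike and differ in content:

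- Treatment group is the randomized assignment: "Treatment group is defined as planned randomized treatment sequence".
- Treatment arm is drug exposure: "Treatment arm is defined as administration drug group regardless 1st line or 2nd line treatment". The membership rules follow: "That is enzalutamide plus ADT arm include subject who receive enzalutamide plus ADT at 1st line and 2nd line", and "Flutamide plus ADT include who receive flutamide plus ADT at 1st line and 2nd line".

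The neighbouring baseline tables use the first term. SAP 7.2.5 reads "Previous therapies for prostate cancer will be summarized by treatment group as randomized for the ITT population and SAF population", and SAP 7.2.2 (demographics) and 7.2.6 (prior surgery) do the same. Protocol 7.2.1 has the ITT population analysed by randomized group, and Protocol 7.3 summarizes baseline characteristics by treatment group. SAP 7.1.1 makes the planned group the default for ITT summaries, but lets a specific statement override it.

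The SAP also defines previous medication twice. Section 6.5 has a window: "Previous medication is defined as medication with at least one dose taken 4 weeks (28 days) before Day 1", running to the day before the first study dose. Section 7.2.4 has none: "Previous medication is defined as medication with at least one dose taken before initial study treatment".

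**The concern.** Previous medication is fixed before treatment starts. A reader uses such a table to see whether randomization left the groups alike, which requires one column per randomized group, with each subject counted once. Columns defined by later drug exposure do not give that. They overlap, and their membership depends on who went on to 2nd line, which is decided after randomization. They also have no place for an ITT subject who took no study drug, although the table is specified for that population.

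At stake is one descriptive display. If the groups differed at entry in general medication, the display would understate the difference by an amount the reader could not judge from the table itself. SAP 7.2.5 does not replace it, because that section covers therapies for prostate cancer.

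**Working it through.** The plan states no figure on this point, so there is none to reproduce. The check is column arithmetic under the SAP's own definitions.

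**Inputs**

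- Group size n = 100 per group, 1:1 (SAP Section 4).
- Group A takes enzalutamide, then flutamide. Group B takes the reverse (SAP 3.2).
- Column membership: any receipt of the drug, in either line (SAP 7.1.2).
- Assumed: cA and cB, the shares of A and B that start the second drug. The documents give no rate, so a range is shown.
- Assumed for illustration: pA = 40% and pB = 20% took a given previous medication, a true difference of 20 points.
- Assumed: all subjects receive the assigned first drug, and switching is unrelated to medication use.

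**Formula**

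The enzalutamide column holds n(1 + cB) subjects, of whom n(pA + cB·pB) took the medication. The flutamide column holds n(1 + cA), of whom n(pB + cA·pA) took it. The displayed difference is

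(pA + cB·pB)/(1 + cB) − (pB + cA·pA)/(1 + cA) = (pA − pB)(1 − cA·cB)/[(1 + cA)(1 + cB)].

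With cA = cB = c the multiplier reduces to (1 − c)/(1 + c).

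**Results, equal switching**

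| c | Each column | In both columns, of 200 | Multiplier | 20 points shows as |
|---|---|---|---|---|
| 0.3 | 130 | 60 | 0.7/1.3 = 0.538 | 10.8 |
| 0.5 | 150 | 100 | 0.5/1.5 = 0.333 | 6.7 |
| 0.7 | 170 | 140 | 0.3/1.7 = 0.176 | 3.5 |
| 0.9 | 190 | 180 | 0.1/1.9 = 0.053 | 1.1 |
| 1.0 | 200 | 200 | 0 | 0 |

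**Unequal switching.** With cA = 0.4 and cB = 0.8 the multiplier is (1 − 0.32)/(1.4 × 1.8) = 0.68/2.52 = 0.270. The 20 points show as 5.4, in columns of 180 (enzalutamide) and 140 (flutamide).

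**Switching related to medication use.** The simple formula then fails.

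- If every user and 60% of non-users switch, the columns read (40 + 20)/(100 + 20 + 48) = 35.7% and (20 + 40)/(100 + 40 + 36) = 34.1%, a difference of 1.6 points.
- If 30% of users and 80% of non-users switch, they read (40 + 6)/(100 + 6 + 64) = 27.1% and (20 + 12)/(100 + 12 + 48) = 20.0%, a difference of 7.1 points.

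The display then depends on who switched as well as on how many.

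**After the change.** By randomized group, the columns are 100 and 100 with no overlap, and the 20 points show in full.

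**The two definitions.** Protocol 5.1.3.1 collects general previous medication only from 28 days before Day 1, so for those drugs SAP 6.5 and 7.2.4 select essentially the same records. Bicalutamide and other prostate cancer drugs are collected from diagnosis. If those records entered the table, the definitions would diverge. Prior bicalutamide would count for essentially everyone under 7.2.4, and for no eligible subject under 6.5, because Protocol 3.3 excludes its use within 6 weeks before Day 1.

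**The case against.** **The wording may only be loose.** The table is specified for the ITT population, which SAP 5.1 analyses by randomized group, and an exposure-based ITT table with no column for undosed subjects is odd enough to suggest a slip. SAP 7.5.1 itself mixes the terms, setting treatment-group thresholds for tables organized by arm. Column layouts sit in the table specifications, which are not among these documents. All of this stands as doubt about intent. It does not change what the text instructs: the term is defined, the default in SAP 7.1.1 yields to a specific statement, and a programmer following SAP 7.1.2 would build overlapping columns.

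**Most relevant drugs appear elsewhere.** A reader might infer that an imbalance in bisphosphonate, denosumab or low-dose steroid use at entry would be hidden. The documents do not support that. These drugs are permitted within stated limits and are usually ongoing. A drug continued past the first dose falls in the 1st-line concomitant set that SAP 7.2.4 defines separately. Within 1st line, the arm is the dosed randomized group provided subjects take the assigned drug, so a difference there is not diluted. This objection largely stands. It leaves drugs stopped before the first dose, and the separation of pre-existing from newly started drugs.

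**The table feeds nothing.** It enters no test, model or listed subgroup, and listings of previous and concomitant medications are planned. This also stands.

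**Conclusion.** The point holds as a minor one. As written, SAP 7.2.4 displays a pre-treatment variable in overlapping exposure columns, out of line with Protocol 7.2.1 and 7.3 and with SAP 7.2.2, 7.2.5 and 7.2.6.

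How far a true difference is diluted depends on the switching rate, which the documents do not give. Under equal switching unrelated to medication use, between about half of it (c = 0.3) and none of it (c = 1.0) remains visible.

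A reader might infer that the table can show no imbalance at all, or that its columns are mostly the same people. The first is true only at complete switching. The second presumes a high rate, and the documents contain limits on switching: Protocol 3.4 bars the 2nd line for some subjects and leaves other cases to the investigator.

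No efficacy conclusion is affected. The mismatch between the two definitions of previous medication is real but has little effect on general medication, given what the eCRF collects.

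**What to change.** In SAP 7.2.4:

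- Tabulate previous medication by treatment group as randomized, in place of treatment arm.
- Use the 28-day definition of SAP 6.5 and drop the one without a window. Prostate cancer therapies stay in SAP 7.2.5.
- Keep presentation by arm for concomitant medication only, and say explicitly that it is split by treatment line.

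The cost is a few words in the SAP and one table shell, with no new data. If the SAP is not reissued, the change can be justified in the clinical study report, as SAP Section 1 allows.

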7.2.5 Previous Therapies for Prostate Cancer

Previous therapies for prostate cancer will be summarized by treatment group as randomized for the ITT population and SAF population as follows:

- Summary statistics for treatment duration of bicalutamide
- Number of subjects with gonadotropin releasing hormone (GnRH) agonist / antagonist and each drug
- Number of subjects with other drug therapies
- Number of subjects with radiation therapy

7.2.6 Prior Surgical Procedures for Prostate Cancer

Number and percentage of subjects with any prior surgical procedures for prostate cancer (prostatectomy, orchiectomy, transurethral resection of the prostate (TURP), cryoablation, pelvic lymph node dissection, high intensity focused ultrasound (HIFU), and other) will be tabulated by treatment group as randomized for the ITT population and SAF population.

7.3 Study Drugs

7.3.1 Exposure

Duration of exposure will be summarized in two ways for the ITT population and SAF.

- Descriptive statistics will be presented by treatment group and treatment line.
- Exposure time will be categorized according to the following categories by treatment group and treatment line:
 - o less than 3 months
 - o at least 3 months, less than 6 months
 - o at least 6 months, less than 12 months
 - o at least 12 months, less than 24 months
 - o 24 months or more

Counts and percentages of subjects in each of these categories will be summarized for each treatment group.

Total treatment duration will be summarized by treatment group applying same rule as above.

7.3.2 Dose Modification

Subjects with at least one dose modification, including dose reduction and interruption, and the reason for the dose modification (adverse event or other) will be summarized by treatment group and treatment line for the ITT population and SAF. Also, subjects with at least one dose reduction and those reason will be summarized by treatment group and treatment line for the ITT population and SAF.

7.3.3 Treatment Compliance

Treatment compliance will be examined for subjects in the ITT population and SAF. For the details of treatment compliance calculation please refer to section 6.5.

Descriptive statistics will be presented for total number of study drugs taken per subject by treatment group and treatment line.

Percent compliance will be summarized in two ways:

- Descriptive statistics will be presented by treatment group and treatment line.
- Percent compliance will be categorized according to the following categories by treatment group and treatment line:
 - o less than 20%
 - o at least 20%, less than 40%
 - o at least 40%, less than 60%
 - o at least 60%, less than 80%
 - o at least 80%, less or equal to 100%
 - o greater than 100%, less than 120%
 - o greater or equal to 120%

7.4 Analysis of Efficacy

All analysis of efficacy will be presented by planned treatment group for ITT population, unless specified otherwise. The data obtained at Day 1 visit will be used as the baseline for efficacy assessment except for rPFS for which the data at the Screening visit will be used as the baseline.

7.4.1 Analysis of Primary Endpoint

The primary efficacy analysis will be performed on the TTPP1 for the subjects in the ITT population. TTPP1 is the period from randomization to the first day when PSA progression is objectively identified. Convention of censoring is specified in table 7-1.

If a subject meets the criteria for more than one censoring rule, they will be censored with the earliest censoring date. The PSA progression date is the first date where progression definition is met, not confirmed.

Methodology

The benefit of enzalutamide as compared to flutamide will be assessed with the stratified log-rank test as the primary efficacy analysis. The stratification factor will be the disease stages (M0/N0, M0/N1, or M1) used as stratification factor for allocation.

The hypothesis for comparisons is as follows:

H0: The survival time distribution of enzalutamide group is the same as that with flutamide group.

H1: The survival time distribution of enzalutamide group is not the same as that with flutamide group.

The significance level is 0.05 (two-sided). ITT is used for the primary analysis.

Unstratified Cox's Proportional Hazards Model with treatment and disease stage as the covariate will be used to support the log rank test.

The benefit of enzalutamide compared to flutamide will be evaluated by hazard ratio (enzalutamide/flutamide) with its 95% confidence interval (CI) based on Cox Proportional Hazard Model.

Kaplan-Meier curves will be used to estimate the distribution of duration of TTPP1 and Stratified curve will be estimated by disease stage. The 50th percentile of Kaplan-Meier estimates will be used to estimate the median duration of TTPP1. A two-sided 95% CI will be provided for this estimate. The 25th and 75th percentiles, and the range (minimum, maximum) will be presented as well. The range will be determined including censored observations. Estimated Kaplan-Meier curve will be plotted.

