7.1 Sample Size

The number of evaluable subjects will be approximately 200 subjects (1st line AAT enzalutamide group: 100, 1st line AAT flutamide group: 100).

The sample size to evaluate the time to PSA progression with 1st line AAT (TTPP1), which is the primary endpoint of the study, was calculated in consideration of the following points:

- Median TTPP1 with enzalutamide: 10.5 months.
- Median TTPP1 with flutamide: 6 months. Values reported in the literature: 5 months according to [Okihara et al., 2007], 6.25 months according to [Narimoto et al., 2010].
- The ratio of randomization of 1st line AAT enzalutamide and flutamide groups is 1:1.
- Subject enrollment period is 12 months, and the observation period is 24 months from the enrollment of the last subject.
- Type I error of the two-sided test is 0.05, and power is 90%.
- A log-rank test with the TTPP1 parameters shown above requires 135 events. The necessary number of subjects calculated based on the required number of events is 74 subjects per group.

Required number of events and necessary number of subjects above are calculated with the formulas below based on [Schoenfeld, 1983]. The codes in the formulas are defined as follows.

 M_t : Median TTPP1 in enzalutamide group

 M_c : Median TTPP1 in flutamide group

 t_a : Enrollment period

 t_f : Observation period from the last subject enrollment

 $Z_{1-\alpha}$: 1- α % point of standard normal distribution

 $Z_{1-\beta}$: 1- β % point of standard normal distribution

[figure not shown]
Hazard in enzalutamide group $(H_t) = \frac{\log_e 2}{M_t}$ Hazard in flutamide group $(H_c) = \frac{\log_e 2}{M_c}$ Hazard ratio for enzalutamide group/flutamide group $(HR) = \frac{H_t}{H_c}$ Required number of events $(N_d) = \frac{4 \times (Z_{1-\alpha} + Z_{1-\beta})^2}{(\log_e HR)^2}$ *The number after the decimal point will be rounded up to the nearest integer. Incidence of events of enzalutamide group $(P_t) = 1 - \frac{1}{6} \left(\exp(-H_t \times t_f) + 4 \times \exp\left(-H_t \times (t_f + \frac{1}{2} \times t_a)\right) + \exp\left(-H_t \times (t_f + t_a)\right) \right)$ Incidence of events of flutamide group

$$(P_c) = 1 - \frac{1}{6} \left(\exp\left(-H_c \times t_f\right) + 4 \times \exp\left(-H_c \times (t_f + \frac{1}{2} \times t_a)\right) + \exp\left(-H_c \times (t_f + t_a)\right) \right)$$

Incidence of events of both groups $(P) = \frac{1}{2} \times (P_t + P_c)$

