7.4.2.7 Radiographic Progression-Free Survival (rPFS)

The rPFS is defined as the time from randomization to the first objective evidence of radiographic disease progression assessed by the blinded independent central review facility or on-study death, defined as death within 28 days after treatment discontinuation, whichever occurs first. rPFS will be assessed in the ITT population. Radiographic disease progression will include soft tissue disease progression and confirmed bone disease progression. The censoring rules are shown in Table 7-1. The analysis of rPFS will be presented by planned treatment group for subjects that having least one distant metastasis at baseline in ITT population.

rPFS will be assessed using the same method as that with TTPP1. i.e. Stratified log-rank test and unstratified cox regression will be applied to rPFS and estimate the distribution using Kaplan-Meier method.

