7.8 Subgroups of Interest

Primary efficacy endpoint, TTPP2, PSA Response Rate to 1st Line AAT, PSA Response Rate to 1st Line AAT at Week 13 and rPFS, analyses will be repeated by the subgroups defined on the basis of the categorized variables listed below:

- Baseline ECOG performance status (0 vs \geq 1)
- Age category (<75 and ≥ 75 years), (at or below median vs above median)
- Total Gleason score (≤ 7 and ≥ 8) at diagnosis
- Type of progression (PSA progression only vs radiographic progression with or without PSA progression) at study entry
- Baseline PSA value (at or below median vs above median)
- PSA value at initial diagnosis (at or below median vs above median)
- Baseline LDH value (at or below median vs above median)
- Baseline hemoglobin value (at or below median vs above median)
- Baseline ALP value (at or below median vs above median)
- Treatment duration of bicalutamide (at or below 12 months vs above 12 months), (at or below median vs above median)
- PSA nadir value on CAB therapy ($\leq 4 \text{ng/mL vs} > 4 \text{ng/mL}$), ($\leq 0.2 \text{ng/mL vs} > 0.2 \text{ng/mL}$)
- PSA response rate to 1st line AAT at Week 13 (below 50% vs at or above 50% reduction from baseline), (below 90% vs at or above 90% reduction from baseline) *except for the analysis of PSA Response Rate to 1st Line AAT at Week 13.
- Baseline NLR value (at or below median vs above median)
- Baseline testosterone value (at or below median vs above median)
- Treatment duration of first line hormonal therapy (at or below 12 months vs above 12 months), (at or below median vs above median)
- Disease stages (M0/N0 vs M0/N1 vs M1)
- PSA doubling time (at or below median vs above median)

Also, selected safety variables (treatment emergent adverse events) will be summarized by the treatment group for the subgroups defined on the basis of the categorized variables listed below:

- Baseline ECOG performance status (0 vs \geq 1)
- Age category (<75 and ≥ 75 years), (at or below median vs above median)

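### Disease stage is the only prognostic term in the TTPP1 and rPFS models; it is essentially constant in the rPFS set, and collected baseline factors are not used as covariates

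*SAP*

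**What the plan says.** **TTPP1.** The primary analysis is a log-rank test stratified by stage (M0/N0, M0/N1, M1). The hazard ratio comes from an unstratified Cox model, of which SAP 7.4.1 says: "Proportional Hazards Model with treatment and disease stage as the covariate will be used to support the log rank test". Protocol 7.4.1.2 likewise adjusts for stage alone.

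**rPFS.** SAP 7.4.2.7 limits the population: "The analysis of rPFS will be presented by planned treatment group for subjects that having least one distant metastasis at baseline in ITT population". It then carries over the TTPP1 methods: "Stratified log-rank test and unstratified cox regression will be applied to rPFS". Protocol 7.4.2.7 does the same. SAP 3.2 defines M1 as the presence of distant metastasis.

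**Other baseline factors.** SAP 7.2.2 summarises baseline PSA, LDH, hemoglobin, ALP and ECOG. SAP 7.8 uses each as a subgroup factor for TTPP1 and rPFS, for example "Baseline PSA value (at or below median vs above median". It also lists disease stage as a subgroup factor for those endpoints. SAP 7.2.3 records disease localization at screening (bone only, soft tissue only, both, or none). None of these factors other than stage enters a Cox model.

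**The concern.** For rPFS, the plan describes a stratified test and an adjusted model, but the population restriction removes the variation in the one factor used. A report that follows the SAP would call the rPFS analysis stratified and stage-adjusted when it is neither. The rPFS subgroup analysis by stage would have only one populated level.

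For TTPP1, the minimization balances facility and stage (SAP 3.3), so balance on PSA, ECOG, LDH, ALP and hemoglobin is left to chance with about 100 subjects per group. Splitting subgroups on these factors does not adjust the overall hazard ratio. Baseline PSA is also tied to the endpoint by its definition, because progression needs both a 25% rise and a 2 ng/mL rise. If the factors are prognostic, a model that includes them has a more powerful treatment test than the stage-only model.

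**Working it through.** **1. The plan's own figure (Protocol 7.1, SAP 4).** Inputs: "Median TTPP1 with enzalutamide: 10.5 months"; "Median TTPP1 with flutamide: 6 months"; allocation 1:1; two-sided 0.05; power 90%; 12 months of enrollment and 24 months of further observation.
- HR = 6/10.5 = 0.571; ln HR = −0.5596.
- Events = 4 × (1.960 + 1.282)² / 0.5596² = 134.2, rounded up to 135. This reads the printed Z(1−α) as the two-sided quantile.
- Event probabilities from the protocol's formula: 0.858 (enzalutamide) and 0.966 (flutamide), mean 0.912. Subjects per group = 0.5 × 135 / 0.912 = 74.0, that is 74.
- 74 / 0.75 = 98.7, against 100 enrolled per group.
- Power at 135 events: Φ(√135 × 0.5596/2 − 1.960) = Φ(1.291) = 0.902.

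The stated design reproduces and takes no credit for covariates.

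**2. rPFS, by definition.** The set consists of subjects with distant metastasis at baseline, and M1 means distant metastasis. All subjects should therefore be M1. A log-rank test with one stratum is the unstratified test, and a constant covariate drops out of the Cox model. The only exceptions would be subjects whose stage at allocation disagrees with their baseline imaging. The documents give no rPFS event count or effect size, so no rPFS power can be computed.

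**3. Baseline PSA and the TTPP1 definition.** For a subject with no Week 13 decline, the reference is baseline. The 2 ng/mL rule governs below 8 ng/mL, because 25% of 8 is 2. From 2 ng/mL, PSA must reach 4, which is log₂(4/2) = 1.00 doubling. From 8 ng/mL it must reach 10, which is log₂(10/8) = 0.32 doublings. At equal exponential growth the required time differs about threefold. For subjects with a decline the reference is the nadir, so the link is weaker.

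**4. Effect of adding five covariates to the TTPP1 model (simulation).** Assumptions not in the documents:
- exponential times;
- five independent normal covariates with equal effects;
- a stage mix of 40/15/45%, with a stage log HR of 0.3 per level;
- a data cut at the 135th event;
- SD of the combined covariate log-hazard from 0 to 0.8.

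Each setting used 200 subjects and 2,000 runs. The Monte Carlo error at a power of 0.89 is √(0.89 × 0.11/2000) = 0.007. The treatment effect was set so that the stage-adjusted HR stayed near 0.571. Stage entered both Cox models as indicators.

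| SD | Stratified log-rank power | Stage-only Cox power | Adjusted Cox power | Mean HR, stage-only / adjusted | SE of log HR, stage-only / adjusted |
|---|---|---|---|---|---|
| 0 | 0.892 | 0.891 | 0.886 | 0.571 / 0.565 | 0.176 / 0.180 |
| 0.2 | 0.890 | 0.893 | 0.903 | 0.566 / 0.552 | 0.176 / 0.180 |
| 0.4 | 0.892 | 0.892 | 0.926 | 0.569 / 0.539 | 0.176 / 0.181 |
| 0.6 | 0.881 | 0.883 | 0.954 | 0.570 / 0.513 | 0.176 / 0.182 |
| 0.8 | 0.882 | 0.887 | 0.973 | 0.573 / 0.489 | 0.176 / 0.183 |

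The SE rises by 2% (0.180/0.176) to 4% (0.183/0.176). With 148 subjects it rises by up to 6% (0.189/0.178). The power gain comes from the hazard ratio, not from a narrower interval.

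**5. Sensitivity to what 0.571 means.** If 0.571 is taken as the covariate-conditional HR, log-rank against adjusted Cox power with 200 subjects is 0.898 vs 0.902 (SD 0.2), 0.842 vs 0.888 (SD 0.4) and 0.798 vs 0.886 (SD 0.6).

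**The case against.** The strongest case against is that nothing planned is lost. The primary test is the stratified log-rank, and changing a supportive Cox model leaves its power exactly where it was. The planning hazard ratio comes from whole-group medians, which read naturally as marginal; on that reading log-rank power stays at 0.88–0.89 at every SD tried. All of this stands.

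A reader might infer several stronger conclusions that the documents do not support:
- *The primary test is underpowered.* This needs the conditional reading in step 5 and a prognostic strength that the documents do not give. At SD 0.2 there is almost no difference.
- *The baseline factors go unused.* They are summarised and are prespecified subgroup factors; they are absent only as covariates.
- *Adjustment would give a more precise hazard ratio.* The SE of the log HR rises.
- *The stage-only hazard ratio is biased towards 1.* It is a different and legitimate estimand from the conditional one.
- *The rPFS test is invalid.* A log-rank test with a single stratum is a valid test. The fault is in the description and in an adjustment that does nothing.

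Timing also deserves weight. The study is open-label, its planned period ended in March 2020, and SAP 1.00 is dated 8 July 2020. Covariates added late can look data-driven. That argues for a short fixed list, settled before lock, and for keeping the protocol's model, rather than against the addition. Eligibility (ECOG 0 or 1, worst pain below 4, life expectancy of at least 12 months) may also narrow the spread in risk and so reduce the gain.

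**Conclusion.** The point holds as a gap in the rPFS specification and an efficiency opportunity for TTPP1. The rPFS part follows from the plan's own definitions and needs no assumption about prognostic strength: stage does essentially nothing in that test, model or subgroup split, apart from any staging mismatch. For TTPP1, the covariate-adjusted Cox test has power of 0.89–0.97 against 0.88–0.89 for the stratified log-rank, a difference of about 0 to 9 points with 200 subjects. That range rests on the assumed SD of 0 to 0.8, the simulated stage mix and covariate structure, and the planning hazard ratio being read as stage-adjusted. The primary test and its sample size are not called into question.

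**What to change.** **TTPP1.** Keep the stage-stratified log-rank test as primary, and keep the protocol's stage-only Cox model. Before database lock, prespecify one supportive Cox model, stratified by stage, with treatment and a fixed list: log baseline PSA (continuous), ECOG 0 vs 1, log ALP, log LDH and hemoglobin. That is six terms for 135 events, or 135/6 = 22.5 events per term. Report the result as a conditional hazard ratio beside the stage-only one. The simulation used stage as indicators; the version stratified by stage was not run separately.

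**rPFS.** State that stage is constant in this set, describe the log-rank test as unstratified, and replace the stage term in the Cox model with log baseline PSA and disease localization (bone only, soft tissue only, both). Remove the rPFS split by stage from SAP 7.8. Say which PSA value is the baseline, because SAP 7.4 names the screening visit as the baseline for rPFS and Day 1 for the other efficacy endpoints.

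**Cost.** A few lines of SAP text, one added TTPP1 model and a changed rPFS model, with no new data. The adjusted hazard ratio is a conditional estimand and must be labelled as such. A few subjects may lack a baseline laboratory value and, with no imputation planned, would drop out of the adjusted model; report how many. If the database is already locked, label the added models post hoc.
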